#### 6.6.1.1. Basic Results

For basic results disclosures in the US and EU the following additional summaries will be provided:

- Treatment Emergent Non Serious Adverse Events by SOC and PT in >5% of patients in either treatment arm;
- Treatment Emergent Serious Adverse Events by SOC and PT; and
- Fatal Adverse Events by SOC and PT.

Each of the above summaries will include a count of the number of patients with all causality events and the number of patients with treatment related events.

CCI [REDACTED]

[REDACTED]

[REDACTED]

[REDACTED]

CCI

### 6.6.1.3. Adverse Events of Special Interest

These analyses will be performed for treatment emergent AEs of special interest as specified in 3.5.1.

- **Time to AE Onset** (in days) is defined as the time from the date of the first dose to the onset date of the AE, regardless of grade. If a patient has multiple episodes of an AE, the date of the first occurrence is used. Time to AE onset (in days) will be calculated as (AE start date – first dose date +1). Time to onset is calculated for the subgroup of patients who had the specific AE.
- **Time to Grade 3 or 4 AE Onset** (in days) is defined similarly as time to AE onset for Grade 3 or 4 AEs.
- **Duration of AE** (in days) is defined as the cumulative duration across episodes of the AE, regardless of grade, where duration for each episode is the time from the AE start date to the AE end date. For one episode, duration (in days) = AE end date – AE start date + 1. If a patient has multiple episodes of an AE, cumulative duration across all episodes will be used adjusting for any overlap. If a patient has an AE that was ongoing at the time of analysis, the time is censored at the last available on treatment visit date. Duration is calculated for the subgroup of patients who had the specified AE.

Descriptive statistics will be presented for time to AE onset (days), time to Grade 3 or 4 AE onset, and duration of AEs for the subgroup of patients with the AE.

Person-year exposure analyses may also be considered in case of relevant difference in treatment duration between treatment arms.

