### 3.5. Safety Endpoints

Safety endpoints will be summarized based on the on-treatment period unless otherwise specified.

On-treatment is defined as the time from the first dose of study treatment to last dose prior to HSCT + 28 days and if applicable, from first dose post-HSCT to last dose + 28 days or start of new anti-cancer drug therapy (minus 1 day), whichever occurs first. Note that conditioning regimens for HSCT (regardless of whether glasdegib is resumed after HSCT) are not considered “new anti-cancer drug therapy”. Adverse events occurring on the same day as the first dose of study treatment will be considered to have occurred during the on-treatment period. All other assessments which occur on the same day as the first dose of study treatment will be considered baseline assessments (see [Section 3.4](#) for the definition of baseline).

Safety data collected outside the on-treatment period as described above will be listed but not summarized.

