### 5.2.8. Analyses for Continuous Data

Continuous variables will be summarized using descriptive statistics ie, number of non-missing values and number of missing values [ie, n (missing)], mean, median, standard deviation (SD), minimum, maximum and first and third quartile (Q1 and Q3). CCI [REDACTED] PK summaries will also include coefficient of variation percent (%CV).

In case the analysis refers only to certain visits, estimates will be based on the number of patients with an assessment at that visit, unless otherwise specified.

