### 5.2.10. Analyses for Time to Event Data

The stratified log-rank test will be used for comparing treatments. Hazard ratios and the associated 95% two-sided confidence intervals are estimated by Cox proportional hazards (PH) model. Repeated confidence interval will also be provided, to account for alpha spending, when appropriate.

Time to event endpoints will be summarized using the Kaplan-Meier method and estimated survival curves will be displayed graphically when appropriate. Graphs will describe the number of patients at risk over time. The median, first and third quartiles, and probabilities of an event at particular points in time will be estimated by the Kaplan-Meier method. Confidence intervals for medians and quartiles are based on the Brookmeyer-Crowley method. Confidence intervals for the estimated probability of an event at a particular timepoint will be generated using the log(-log) method with back transformation to a confidence interval on the untransformed scale. Summaries of the number and percentages of patients with an event and reason for censoring will also be provided on summary tables and/or figures.

If a cumulative incidence analysis is performed, the stratified Gray's test will be used for comparing treatments. Hazard ratios and the associated 95% two-sided confidence intervals are estimated by a proportional subdistribution hazards model. The 25th, 50th, and 75th percentiles and probabilities of an event at particular points in time will be estimated from the cumulative incidence curve. Confidence intervals for the estimated probability of an event at a particular timepoint will be generated using the delta method with a log(-log) transformation for the standard error.

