**AE Stop Date:**

Ongoing events will have the AE Stop Date set to one of the following values:

- Date of Death, if the patient died and a date of death exists.
- Maximum of (Patient Withdraw date, AE Onset Date, AE Collection Date) if the patient withdrew from the study and a date of withdraw exists.
- Maximum of (AE Onset Date, Subject Summary Collection Date, AE Collection Date) if the Disposition CRF page for the long-term follow-up phase exists but a date of completion/discontinuation does not exist.
- Maximum of (Last Treatment Date, AE Onset Date) if no Disposition CRF page for the long-term follow-up phase exists.

Imputation will only occur if event is unique for the patient, or it is the last of a series of similar events; otherwise the Stop Date will not be imputed. Adverse Events are deemed similar if they have the same verbatim term.

Resolved events will have the AE Stop Date set to the maximum of the AE collection date and the AE Onset date.

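### Durations of ongoing adverse events of special interest are censored, then summarised as if complete, and a second stop-date rule conflicts with the censoring date

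*SAP*

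**What the plan says.** SAP 6.6.1.3 defines AE duration in patients who had the event. It "is defined as the cumulative duration across episodes of the AE, regardless of grade", with each episode counted as end date minus start date plus one day. For an event ongoing at the analysis, "the time is censored at the last available on treatment visit date". The planned output is: "Descriptive statistics will be presented for time to AE onset (days), time to Grade 3 or 4 AE onset, and duration of AEs", again restricted to patients with the event.

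Two general sections could govern that output. SAP 5.2.8 states that "Continuous variables will be summarized using descriptive statistics" and lists numbers missing and non-missing, mean, median, SD, minimum, maximum and quartiles. SAP 5.2.10 states that "Time to event endpoints will be summarized using the Kaplan-Meier method" and adds counts of events and reasons for censoring. Section 6.6.1.3 cites neither, but its wording is that of 5.2.8.

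SAP 5.3.1 (AE Stop Date) has its own rule: "Ongoing events will have the AE Stop Date set to one of the following values". Depending on the patient's status, the value is the death date, the latest of several withdrawal, onset or collection dates, or the later of the last treatment date and the onset date. SAP 5.3 places imputations in the analysis datasets.

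**The concern.** Censoring has meaning only if the summary uses it. A mean or median taken over all recorded times treats an event that was still running at the cut-off like one that had resolved. The table would then report durations that are too short, and nothing in it would show how many were cut off. If the share ongoing differs between arms, for example because treatment duration differs, the arms could look different for that reason alone. The 5.3.1 imputation has the same effect by another route: it gives an ongoing event a stop date and so makes it look complete.

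What is at stake is the accuracy of one descriptive safety table. No test of AE duration is planned.

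**Working it through.** The documents give no AE durations and no share of events ongoing, so there is no plan figure to reproduce. The check has three parts.

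**1. Does the planned summary use the censoring?** No statistic listed in 5.2.8 takes a censoring indicator. The visible text of 6.6.1.3 asks for no flag, no count of ongoing events and no separate summary of resolved events. By contrast, SAP 6.2.3 names Kaplan-Meier explicitly for duration of response. Applied as written, 6.6.1.3 summarises the recorded time Y = min(T, C), where T is the true duration and C the time to censoring.

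**2. Direction and size.** Y cannot exceed T, so recorded durations can only be too short. For size, assume a single interval, exponential T with mean 60 days, and independent exponential C giving censored share c. Then Y is exponential with mean 60 × (1 − c). The true median is 60 × ln 2 = 41.6 days, and the naive median is 41.6 × (1 − c).

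| Share ongoing (assumed) | Naive mean, days | Naive median, days |
|---|---|---|
| 10% | 60 × 0.9 = 54 | 37.4 |
| 30% | 60 × 0.7 = 42 | 29.1 |
| 50% | 60 × 0.5 = 30 | 20.8 |

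A simulation of 200,000 durations gave the same values to within about 0.1 day. With Weibull durations (shape 0.7 to 1.5, independent exponential censoring) the naive mean was low by 7–15% at 10% ongoing, 23–42% at 30% and 39–65% at 50%. For these single intervals the Kaplan-Meier median matched the true median to within about 0.1 day.

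The median result depends on the censoring pattern. If all patients share one fixed censoring time and no more than half the events are ongoing, the naive median equals the true median, because cutting off the upper tail does not move the middle value. In the exponential case the mean still falls to 60 × (1 − c).

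**3. Do the two stop-date rules agree?** For a patient who dies with the event ongoing, 6.6.1.3 ends the duration at the last on-treatment visit and 5.3.1 ends it at death; the results differ by the gap between those dates. For a patient with no long-term follow-up disposition page, 5.3.1 uses the later of last treatment and onset, which is again not a visit date. No text says which rule feeds this table.

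The 6.6.1.3 rule can also fail outright. Under SAP 3.5 the on-treatment period may run "from first dose post-HSCT to last dose + 28 days or start of new anti-cancer drug therapy", so a qualifying event can start up to 28 days after the last dose. The protocol's schedules of activities place the End of Treatment visit within 14 days of the last dose. If that visit is the last on-treatment visit (an assumption), an event that starts on day 28 after the last dose and is still ongoing has duration 14 − 28 + 1 = −13 days. The last 5.3.1 option guards against this by taking the later of two dates; 6.6.1.3 has no such guard.

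**The case against.** **The method may simply be unstated.** Section 6.6.1.3 lists no individual statistics and does use the word censored, so a programmer could apply 5.2.10. That is possible, but the section names the other method, and a plan should not leave the choice to the programmer. Some text in SAP 3.5.1 and just before 6.6.1.3 is blacked out, so this reading rests on what is visible.

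**The target may be on-treatment burden.** SAP 3.5 summarises safety over the on-treatment period. On that view the cut-off time is what is wanted: observed days with the event while on treatment. This is a legitimate quantity, but calling it censored points to time to resolution. If burden is meant, the SAP should say so.

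**The specific rule beats the general one.** Section 6.6.1.3 would ordinarily prevail over 5.3.1. That narrows the conflict without settling it, since imputed dates sit in the analysis datasets.

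**The remedy is imperfect.** This stands. Duration is summed over episodes, so the time scale has gaps, and a patient who is between episodes at the cut-off counts as complete although more may follow. In one illustrative recurrent-episode simulation with assumed inputs (true median about 36 days), Kaplan-Meier gave 31 days at 15% ongoing and 25 at 30%, against 26 and 18 for the naive median. Only the ordering should be taken from this. Death or discontinuation may also make the censoring informative.

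**Stronger readings to avoid.** A reader might infer from the table above that arms at 30% and 50% ongoing with identical true durations would differ by about 8 days in the median. That holds only for the assumed model. Nor do the documents support 30–50% ongoing: toxicities that continue after treatment stops are followed at least every 4 weeks until resolution or until no further improvement is expected. A reader might also infer consequences for labelling or for muscle spasm. The list of events of special interest is in a separate document, and no text ties AE duration to labelling.

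**Conclusion.** The point holds as an analysis flaw in a descriptive safety table. Read with 5.2.8, section 6.6.1.3 turns censored times into completed durations and does not show how many are affected. The direction is downward; the size is unknown. Proportional shrinkage of both mean and median by the censored share rests on exponential durations, independent exponential censoring and a single interval per patient. The second finding, that 5.3.1 and 6.6.1.3 give different end dates for the same ongoing event, needs no numerical assumption.

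The optional exposure analysis ("Person-year exposure analyses may also be considered in case of relevant difference in treatment duration between treatment arms") does not help: it adjusts for time on treatment and does not address censored durations. There is no effect on OS, alpha, power or sample size, and the priority is low.

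**What to change.** Amend SAP 6.6.1.3 to say that:

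- AE duration is summarised by the Kaplan-Meier method of 5.2.10 (median, quartiles, 95% CI), with ongoing events censored at one stated date that cannot precede onset;
- the number and percentage of patients with an ongoing event are shown by arm beside the estimate;
- the 5.3.1 stop-date imputation is not used for this analysis.

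Because Kaplan-Meier on cumulative time may leave some bias, the estimate should be read with the number ongoing. Duration of the first episode could be added as a supportive summary. If on-treatment burden is intended instead, the section should say so and drop the word censored. Descriptive statistics for resolved events alone would be a weaker choice, because resolved events are selected towards short ones.

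The cost is a sentence or two in the SAP and one standard table. No new data are needed.

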Following Chemotherapy or HSCT, glasdegib or matching placebo may be permanently discontinued as described in [Section 6.5](#). Subject will discontinue blinded therapy if disease status is MRD-negative post consolidation or HSCT by 2 consecutive timepoints per central laboratory results. Subjects will then enter the post treatment follow-up phase for survival assessments.

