In the Phase 1b portion of Study B1371003 for glasdegib in combination with 7+3, the PK of 100 mg QD glasdegib at steady state were in line with expected exposures and the exposures of 7+3 were in line with historically reported exposure data.

The safety profile of the addition of glasdegib to LDAC was generally tolerable and manageable. Despite the differences in treatment and follow-up duration between the two arms, increases in cytopenias were not accompanied by significant increases in sepsis or bleeding. The principle SMO inhibitor toxicities of dysgeusia, alopecia, and muscle spasms were mostly Grade 1 or 2 in severity and manageable with continued dosing with or without dose modification.

Improvements in response rates, reductions in disease relapse frequency, and improvements in OS in the context of historical controls have been observed both in different populations (MDS, post-allogeneic stem cell transplant (SCT), and elderly patients with AML suitable for intensive chemotherapy) and with different AML treatment regimens commonly used in the treatment of AML patients (azacitidine, decitabine, '7+3', allogeneic SCT).

The clinical safety database of glasdegib contains over 300 patients with hematologic malignancies who received the glasdegib recommended daily dose of at least 100 mg. The safety profile observed so far appears consistent with that reported for the SMO inhibitor class and the underlying chemotherapy backbones.

Based on the results from B1371003, 2 prospective randomized (1:1), double-blind, placebo-controlled registration trials in patients with newly diagnosed AML are proposed: in the first study, 400 AML patients suitable for intensive chemotherapy will be randomized to receive '7+3'+ glasdegib (Arm A) or '7+3'+ placebo (Arm B). In the second study, 320 AML patients not suitable for intensive chemotherapy per investigator will be randomized to receive azacitidine + glasdegib (Arm A) or azacitidine + placebo (Arm B). The primary endpoint for both trials will be OS. Both studies will be powered, conducted, and analyzed separately and independently under 1 protocol (B1371019) to maximize efficiency. Together, the trials can provide substantial evidence to register glasdegib in AML patients treated in combination with 7+3 or with azacitidine.

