#### **Non-Intensive Chemotherapy Study:**

Subjects will be stratified at randomization by genetic risk (favorable vs intermediate vs adverse by ELN genetic risk categories) and age ( $<75$  years vs  $\geq 75$  years).

A total of 320 subjects who are not candidates to receive Intensive Chemotherapy will receive treatment as follows:

- Experimental Therapy: Glasdegib 100 mg PO QD or matching placebo is to be administered by mouth daily beginning on Day 1 of chemotherapy and will continue if subjects demonstrate reasonable evidence of clinical benefit and do not meet the criteria for progression regardless of any delays/modifications in the chemotherapy treatment. Subjects will continue glasdegib or placebo until disease progression, unacceptable toxicity, consent withdrawal, or death, whichever comes first.
- Azacitidine will be administered by subcutaneous injection (SC) or intravenous (IV) infusion daily for 7 days, in 28 day cycles for as long as they do not meet the criteria for disease progression, unacceptable toxicity, consent withdrawal, or death, whichever comes first.
- Alternate dosing schedules to administer the 7 doses of azacitidine to accommodate patient and treatment center availability is allowed. Dose adjustments will be made according to local approved label for azacitidine. In addition, each subsequent cycle may be delayed for up to 28 days to allow for recovery of blood counts. Patients should continue to receive treatment as long as they do not meet the criteria for progression.
- Per Investigator discretion, HSCT may be performed. Glasdegib or placebo will be interrupted at least 28 days before HSCT Day 0 (day of stem cell infusion), and resumed 30-60 days post HSCT after documentation of ANC engraftment ( $\geq 0.5 \times 10^9/L$  for 3 consecutive days without growth factor support), no ongoing  $\geq$  Grade 2 GVHD, and no ongoing SAEs that prevent resumption of glasdegib/placebo in the judgement of the Investigator. If therapy is resumed, glasdegib/placebo may continue up until 2 consecutive CR MRD-negative results, death or consent withdrawal.
- For patients undergoing HSCT, azacitidine may continue prior to HSCT, per the investigator discretion. Following HSCT, azacitidine will not be resumed.

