#### **5.5.1.1. Glasdegib or Placebo in Subjects Receiving Intensive Chemotherapy and Non-Intensive Chemotherapy**

Study treatment (glasdegib or placebo) will be administered by mouth at a starting dose of 100 mg daily at approximately the same time each day, preferably in the morning with approximately 8 ounces (240 ml) of water. Study treatment can be administered with or without food. Tablets must not be crushed or cut; they must be swallowed whole and not chewed.

A cycle is defined as 28 days, in the Non-Intensive Chemotherapy study. There is up to a 28 day window to coincide with azacitidine administration; dose delays due to toxicity will not impact the cycle duration or planned protocol assessments.

If a subject forgets to take their dose at the regularly scheduled time, and if less than 10 hours have passed since the scheduled dosing time, that dose should be taken as soon as possible. If more than 10 hours have passed since the scheduled dosing time, the dose should be skipped and the subject should continue on their normal dosing schedule. If a subject misses a day's dose entirely, they must be instructed not to "make it up" the next day. Missed doses will NOT be made up at any time. If a subject vomits any time after taking a dose, they must be instructed not to "make it up," but to resume subsequent doses the next day as prescribed. If a subject inadvertently takes one extra dose during a day, the subject should not take the next day's dose of glasdegib or placebo.

[figure not shown]
During the intensive chemotherapy study, glasdegib/placebo dosing will begin on Day 1 and be given once daily continuously in combination with Induction and Consolidation chemotherapy. Glasdegib or placebo will continue to be administered for a maximum of 2 years (starting from randomization until 2 years) or until subject discontinues per [Section 6.5](#), or until confirmed CR MRD negative with two consecutive central laboratory results post consolidation.

During the non-intensive chemotherapy study, glasdegib or placebo dosing will begin on Day 1 and will be given once daily with azacitidine in 28 day cycles or until subject discontinues per [Section 6.5](#), or is confirmed CR MRD negative by two consecutive central lab results post HSCT.

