#### **6.6.1. Adverse Events**

All analyses will be based on treatment emergent events unless otherwise specified. Treatment emergent is defined in [Section 3.5.1](#).

A high level summary of adverse events will include the number and percent of patients with:

- Any Adverse Event;
- Serious AE;
- Adverse Events with maximum CTCAE Grade 3-4;
- Grade 5 events;
- AEs leading to dose interruptions separately for each study drug, for chemotherapy, and for any study treatment;

- AEs leading to dose reductions separately for each study drug, for chemotherapy, and for any study treatment;
- AEs leading to withdrawal separately for each study drug, for chemotherapy, and for any study treatment.

Additionally, the number of events reported for each of the categories above will be provided. Each unique adverse event at the PT level in each treatment arm of the study for a patient is included in the count.

Seriousness, toxicity grade, action taken (interruption, reduction, and withdraw) are as reported by the investigator on the adverse event CRF.

Summaries by treatment arm, SOC and PT in decreasing frequency based on the frequencies observed in the glasdegib arm will be provided for:

- Treatment Emergent Events by Maximum Toxicity Grade (All Causality);
- Treatment Emergent Events by Maximum Toxicity Grade (Treatment Related);
- Serious Treatment Emergent Events by Maximum Toxicity Grade (All Causality);
- Serious Treatment Emergent Events by Maximum Toxicity Grade (Treatment Related).

An event will be considered treatment related if the investigator considered the event related to the study drug or this information is unknown.

The above four summaries will also be provided separately for (1) treatment emergent events prior to HSCT, (2) non-treatment emergent events during HSCT, and (3) treatment emergent events after HSCT.

The following summaries will be provided by treatment arm and PT (ie, summaries will not include SOC) in decreasing frequency based on the frequencies observed in the glasdegib arm for:

- Treatment Emergent Events (All Causality) Experienced by  $\geq 10\%$  of patients in either treatment arm;
- Treatment Emergent Events (All Causality) by Preferred Term and Maximum Toxicity Grade;
- Treatment Emergent Grade 3-5 Events (All Causality) by Preferred Term and Maximum Toxicity Grade;

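### Adverse-event percentages depend on time on treatment, and the plan leaves exposure adjustment optional and undefined

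*SAP*

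**What the plan says.** SAP 3.5 sets the safety window: "On-treatment is defined as the time from the first dose of study treatment to last dose prior to HSCT + 28 days". It reopens at the first dose after transplant and closes 28 days after the last dose "or start of new anti-cancer drug therapy (minus 1 day), whichever occurs first". Safety data outside it are, as a rule, listed without being summarised.

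Treatment duration follows the same rules in both arms of each study. In the non-intensive study (Protocol 3), "Subjects will continue glasdegib or placebo until disease progression, unacceptable toxicity, consent withdrawal, or death, whichever comes first". In the intensive study (Protocol 5.5.1.1), "Glasdegib or placebo will continue to be administered for a maximum of 2 years", and the Protocol Summary adds: "Subject will discontinue blinded therapy if disease status is MRD-negative post consolidation or HSCT by 2 consecutive timepoints per central laboratory results".

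On reporting, SAP 6.6.1 opens with "A high level summary of adverse events will include the number and percent of patients with" a list of AE categories, and adds event counts. The tables by preferred term and grade, and the disclosure tables in SAP 6.6.1.1, are also counts of patients. Exposure is summarised separately in SAP 6.5.3. An exposure-based AE analysis appears once in the readable text, in SAP 6.6.1.3 on AEs of special interest: "Person-year exposure analyses may also be considered in case of relevant difference in treatment duration between treatment arms". The text between SAP 6.6.1.1 and 6.6.1.3 is redacted.

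**The concern.** Time on treatment is an outcome of randomised treatment. A patient treated for longer is observed for longer and has more opportunity to record an event. Crude percentages then mix the AE rate with the length of observation. If glasdegib prolongs treatment, they overstate its toxicity. If it leads to early stopping, they can hide toxicity.

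This is foreseeable in the non-intensive study: treatment is open-ended and the trial is sized on median survival of 16.2 versus 10.4 months (SAP 5.1.1). The issue is also known to the sponsor, whose account of the earlier low-dose cytarabine comparison in Protocol 1.3.2 is qualified with "Despite the differences in treatment and follow-up duration between the two arms". The SAP sentence on person-years recognises the problem. But it does not say what counts as a relevant difference, which estimator would be used, or whether the serious, Grade 3-5 and withdrawal tables are covered. The decision would be made with durations by arm in view. At stake is the secondary objective of evaluating the overall safety profile in both arms.

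**Working it through.** **1. The plan's own figure.** The survival assumptions used below come from the non-intensive sizing: 220 deaths, 90% power, hazard ratio 0.64, one-sided 0.025. Freedman's formula gives [(1 + 0.64)/(1 - 0.64)]² × (1.960 + 1.282)² = 20.75 × 10.51 ≈ 218.1, so 219 deaths. With the two-look boundaries, power at 220 deaths is 0.909 without the futility rule and 0.905 with it. The stated figure reproduces and is not in dispute.

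**2. Inputs.**
- From the documents: median survival 16.2 vs 10.4 months (non-intensive) and 31.5 vs 21 months (intensive); trial duration 37 months (non-intensive), used as the longest possible exposure; treatment cap 24 months (intensive); 28-day tail, L = 28/30.4375 = 0.92 months.
- Assumed, because the documents give no time on treatment: exponential time on treatment with the median equal to, or half of, median survival in each arm; a constant AE hazard r, identical in both arms. The duration ratio is then 16.2/10.4 = 1.56 or 31.5/21 = 1.50. Survival includes time after treatment stops, so these are upper values.

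**3. Formula.** With k = ln 2 / median and cap C, the crude proportion is

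P = 1 - exp(-rL) × { k/(k + r) × [1 - exp(-(k + r)C)] + exp(-(k + r)C) }.

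Solve for r from the placebo percentage, then apply the same r to the glasdegib arm.

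**4. One case in full.** Non-intensive, medians 16.2 and 10.4, C = 37. A placebo percentage of 30% requires r = 32.8 per 100 person-years (0.0273 per month).
- Placebo: k = 0.0667; braces = 0.718; P = 1 - 0.975 × 0.718 = 0.300.
- Glasdegib: k = 0.0428; braces = 0.639; P = 1 - 0.975 × 0.639 = 0.377.

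The crude risk ratio is 0.377/0.300 = 1.26 with no true difference. Under a constant hazard, expected time at risk is P/r: 0.377/0.328 = 1.15 years and 0.300/0.328 = 0.91 years. Dividing events by person-time returns 32.8 per 100 person-years in both arms, a rate ratio of 1.00.

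**5. Range (glasdegib percentage when the true AE rates are equal).**

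| Assumption | Mean window, months (glasdegib vs placebo) | Placebo 10% | Placebo 30% | Placebo 50% |
|---|---|---|---|---|
| Non-intensive, treatment = survival, cap 37 | 19.5 vs 14.7 | 13.1 | 37.7 | 59.6 |
| Non-intensive, treatment = half of survival, cap 37 | 12.1 vs 8.4 | 14.0 | 38.9 | 60.0 |
| Non-intensive, treatment = survival, no cap | 24.3 vs 15.9 | 14.5 | 39.5 | 60.4 |
| Intensive, treatment = survival, cap 24 | 19.6 vs 17.5 | 11.1 | 33.2 | 54.6 |
| Intensive, treatment = half of survival, cap 24 | 15.7 vs 13.0 | 12.0 | 35.4 | 57.3 |

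**6. Sensitivity.** With smaller duration ratios and the non-intensive placebo medians (10.4 or 5.2 months, no cap), 30% becomes 34.4-34.6% at ratio 1.25 and 31.9-32.0% at ratio 1.10. If all the risk falls in the first 1, 2 or 3 months (medians 16.2 vs 10.4), 30% becomes 30.3%, 30.7% or 31.0%.

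**The case against.** Several stronger readings are tempting, and the documents do not support them.

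- *The windows differ by design.* They do not. Stopping rules are the same in both arms, so windows diverge only if efficacy or tolerability differs. In the intensive study the 2-year cap limits the gap, and stopping on confirmed MRD-negativity could shorten the glasdegib window, so the direction is not fixed.
- *Nothing but crude AE reporting is planned.* The plan also has deaths within 30 days of first dose (SAP 6.6.2), the main AE summaries repeated before, during and after transplant (SAP 6.6.1), laboratory abnormalities by cycle or induction (Protocol 9.5.2), and time to onset and duration for AEs of special interest (SAP 6.6.1.3). The redacted text cannot be checked. None of the readable outputs gives an AE rate, however: the 30-day table covers deaths only, the transplant splits do not equalise follow-up, and onset and duration are computed only among patients who had the event.
- *The trial would declare a false safety signal.* The readable plan makes no between-arm test of AEs. The harm is to interpretation of descriptive percentages.

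On-treatment crude incidence is also a legitimate quantity: the chance of an event while on the regimen. Treatment duration will be tabulated, so readers can see a difference. Exposure-adjusted rates are one remedy among several; cumulative incidence with competing risks is another. All of this stands. It argues for keeping the crude tables and adding to them. It does not justify leaving the addition to a later judgement.

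**Conclusion.** The point holds in a limited form. AE window length depends on time on treatment, the readable committed AE tables have no exposure denominator, and the only readable exposure-based provision is optional, undefined and confined to AEs of special interest.

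With no true difference in AE rates, the crude risk ratio could reach about 1.19-1.42 in the non-intensive study (37-month cap, placebo incidence from 50% down to 5%) and 1.09-1.21 in the intensive study. It stays near 1 for early-onset events. These figures rest on assumed exponential treatment times, a constant hazard and duration ratios taken from the survival sizing, so they illustrate an upper range and do not predict the result. If glasdegib shortened treatment, the distortion would run the other way. The primary analysis is unaffected. This is a cheap improvement, with priority in the non-intensive study.

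**What to change.** In SAP 6.6.1, keep the crude tables and commit to the following whatever difference in duration is observed.

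- **Exposure-adjusted incidence rate per arm:** patients with a first event divided by person-years at risk within the on-treatment period of SAP 3.5 (time outside that period, including any transplant gap, does not count), with the rate difference or ratio and its 95% CI. Apply it to all-causality treatment-emergent AEs, Grade 3-5, serious and fatal events, AEs leading to withdrawal, and AEs of special interest. The non-intensive study comes first; the same tables can be produced for the intensive study.
- **Crude incidence in one common early window,** as a check on the constant-hazard assumption. Weeks 12 (non-intensive) and 8 (intensive) are available as the plan's fatigue landmarks, but any window fixed in advance would serve.
- **Delete the optional person-year sentence** in SAP 6.6.1.3.

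The cost is SAP wording and a few extra tables from data already collected. The downside is that exposure-adjusted rates assume a roughly constant hazard, which is why the early-window table goes with them.
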